## 2.15.6 Analysis of Safety Variables

Safety will be assessed through the degree of pain/discomfort related to the procedure (universal pain scale) and the collection of Adverse Events throughout the course of the study. For each treatment group these variables will be summarized. The summaries will include the number and percent of patients for each outcome. No statistical comparisons will be performed for any of these variables.

## **3.0 RISK ANALYSIS AND MANAGEMENT**

### 3.1 Risk Determination

This device study used in this study does not meet the FDA definition for a Significant Risk Device study per 21 CFR 812.3(m). Therefore, the sponsor determines that this is a non-significant risk device study.

Significant risk device means an investigational device that:

- (1) Is intended as an implant and presents a potential for serious risk to the health, safety, or welfare of a subject;
- (2) Is purported or represented to be for a use in supporting or sustaining human life and presents a potential for serious risk to the health, safety, or welfare of a subject;
- (3) Is for a use of substantial importance in diagnosing, curing, mitigating, or treating disease, or otherwise preventing impairment of human health and presents a potential for serious risk to the health, safety, or welfare of a subject; or
- (4) Otherwise presents a potential for serious risk to the health, safety, or welfare of a subject.

### 3.2 Risk Management

The Investigator in this clinical trial has been invited to participate based on his/her previous experience with the use of the system and/or similar systems and industry experience. Experience with treatments is the most critical element in managing subject risk in this trial.

In addition, as with any study, there is a risk of bias. Objective evaluation methods may be used in conjunction with subjective evaluation methods when feasible. The value of the compensation to the clinical investigator for conducting the study is not influenced by the study outcome. If photographic results are listed as the primary objective, they are to be evaluated by blinded evaluators who did not partake in the study. If information concerning investigator assessment of improvement or investigator satisfaction is collected, then it is not listed as an objective for the study.

All other known risks will be disclosed to the subject via the informed consent process. Since this is an elective procedure and the subjects are volunteers, it can be assumed that their signature on the informed consent is indicative of their agreement to accept the risks involved.

The risks to the subjects who participate in this study are the same as those for the subject undergoing similar non-ablative radiofrequency treatment. It is possible to have an adverse reaction to the Brera/Med 400 device use. There may be some side effects that we don't know about yet.

### 3.3 Risk Analysis

**CONTEXT OF THE PROPOSED INVESTIGATION:**

Radiofrequency (RF) diathermocontraction technology has shown to be a non-invasive effective treatment method for aesthetic applications (such as abdominal fat). RF diathermocontraction technology is a safe method for non-invasive treatment because energy can be precisely delivered through the skin to the subcutaneous fat beneath and contract muscle fibers without damaging the epidermis.

**ASSESSMENT OF RISKS OF THE PROPOSED INVESTIGATION:**

There are two risks identified with the Brera/Med 400 device used in this study. The first risk identified is the safety of treatment with the Brera/Med 400 device. Since the Brera/Med 400 device has not been cleared for use and has limited safety data, optimizing the safety profile is necessary. The second risk identified is the lack of clinical data for evidence of effectiveness of Brera/Med 400 device for muscle stimulation and the treatment of lipolysis. Parameters need to be further investigated to be optimized for efficacious results.

The risk identified with the overall clinical investigation is the integrity of the data collected.

There are multiple clinical mitigation strategies for the risks identified. Proper training on the device and protocol will be performed. Data from prior investigations will be utilized to minimize side effects and optimize treatment outcomes. Monitoring of the study will be implemented to minimize subject and data risks.

**ASSESSMENT OF BENEFITS OF THE PROPOSED INVESTIGATION:**

The subject may or may not have improvement in muscle strength and fat reduction.

**CONSIDERATION OF PATIENT PREFERENCE INFORMATION:**

Many physicians support the use of radiofrequency devices for non-invasive cosmetic treatments due to current patient satisfaction of cosmetic results with the currently available devices. However, there is still a level of interest in novel technologies that could reduce the need for future treatments.

**ASSESSMENT OF UNCERTAINTY:**

There is uncertainty of the safety profile and efficacy results while using the Brera/Med 400 device in this study.

**CONCLUSION:**

This device is determined to be a non-significant risk study and will be using a device not cleared for use by the FDA.

Patient population to be enrolled in this clinical study:

Total anticipated population: 30 Subjects

Age Range: 18 years of age or older

Gender: Male or Female

Condition: Muscle stimulation and abdominal fat.

**4.0 DEVICE DESCRIPTION AND SPECIFICATIONS**

The Brera/Med 400® device used in this study is currently not cleared by the U.S. Food and Drug Administration (the FDA).

Changes to the Brera/Med 400® device are not anticipated during the investigation.

The Brera/Med 400® Device Specifications are:

Radiofrequency Specifications	
Parameter	Specification
Effective Treatment Area	RF MULTIPOLAR™: Three electrodes of 0,785 cm  RF SELECTIVE™: Two electrodes of 3 cm  RF ELECTROPORATOR: Six electrodes of 0,031 cm  RF T-POINT™: 0,126 cm  RF- CAPACITIVE™: 19,00 cm  RF- RESISTIVE™: 19,00 cm  RF- MULTIACTION™ - Resistive : 14,32 cm  Capacitive: 4,9 cm  FPC MATRIX™: 1.2 X 1.2 cm by means of 125 points RF THERMOGYM™: Fixed electrodes - Large 132 cm  Medium 78 cm  Small 36 cm  BQUAD™: 4 electrodes 7cm 
Radio Frequency Power	Up to 400W ± 10%
Output Voltage	137 V RMS @ 47Ω
Mode(s) of Operation	CW/PW or combined
Polarization	Multipolar (multiplex Bipolar), Bipolar, Unipolar
Carrier Frequency	in the range 350kHz -1MHz
Modulation frequency	In the range 1Hz-250Hz
Duty cycle	In the range 1-100%
Combination Treatment	Vibration Massage

## 5.0 MONITORING PROCEDURES

The Sponsor Standard Operating Procedure (SOP) for monitoring the investigative site will be followed. The sponsor will train the site following sponsor SOP's and may be present at initiation of treatment. The sponsor will also monitor the site periodically. The Investigator/Institution will permit trial-related monitoring, audits, IRB/IEC review, and regulatory inspections by providing direct access to source documents. The sponsor may request intermediate data following each visit to evaluate treatment progress. Case Report Forms will be reviewed for current data and Regulatory Binders will also be reviewed for correct documents. The sponsor will collect data at

the end of the follow up period. The sponsor will list the study on clinicaltrials.gov when required by FDA regulations.

The monitoring plan for this study is outlined in the Cynosure Monitoring Plan.

### **6.0 LABELING**

Sample labeling will follow FDA regulations and the sponsor standard operating procedure.

If applicable, the Brera/Med 400® device label will include, (in accordance with 801.1):

Statement: "CAUTION--Investigational device. Limited by Federal (or United States) law to investigational use."

Additionally, the label or other labeling will describe all relevant contraindications, hazards, adverse effects, interfering substances or devices, warnings, and precautions.

Directions for use are contained in the Brera/Med 400® Operator's Manual

### **7.0 CONSENT MATERIALS**

Forms and informational materials which are provided to the subject during the informed consent process are listed below:

Form/Informational Material Description
Pre and Post Treatment Instructions
Informed Consent Form

### **8.0 INSTITUTIONAL REVIEW BOARD INFORMATION**

This protocol, informed consent forms, and any amendments to the protocol will be reviewed by the appropriate Institutional Review Board prior to initiation. The study will not be initiated without the approval from the Institutional Review Board.

## **9.0 OTHER INSTITUTIONS**

If a part of the study is conducted by an institution that has not previously been identified within the Investigational plan each institution's contact information will be documented below;

No other institutions will be part of this study.

## **10.0 ADDITIONAL RECORDS AND REPORTS**

If this is an IDE study, additional records and reports will be maintained on the investigation in addition to those prescribed in 21 CFR 812 sub-part G. If this is a non-IDE study, the study summary will be maintained on the investigation and may include those prescribed in 21 CFR 812 sub-part G.

### **Additional Records and Reports:**

Report	Submit To	Description/Constraints
N/A	N/A	This is a non-IDE study; no additional records or reports will be maintained.

## **11.0 PREGNANCY**

Females may not participate in this study if they are pregnant, breastfeeding, were pregnant within the last three months or are planning a pregnancy during the study.

If the subject thinks they have become pregnant during the study, it is important that they inform the Investigator immediately. If she becomes pregnant or thinks that she may be pregnant, she will be removed from the study and will be asked to perform a final evaluation similar to the final follow-up visit. The Investigator may request to track the pregnancy and will report the pregnancy to the Sponsor.

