## **2.6 Pre-Treatment Procedures**

If the subject is of childbearing potential (i.e. females not post-menopausal or not surgically sterile), pregnancy verification will be required. Pregnancy verification will be performed by asking the subject if they are pregnant, the date of their last menstrual cycle, and be required to perform a urine pregnancy test at the site. For Group A, pregnancy verification will be performed prior to the subject's first treatment and prior to their 5th treatment. Pregnancy verification will be performed by verifying the date of their last menstrual cycle at each subsequent treatment. For Group B, pregnancy verification will be performed prior to the subject's first treatment and prior to each treatment only if their treatment is 30 days past their last pregnancy verification. A urine pregnancy test may also be conducted at the Investigator/clinician's discretion at any time during the study. If a urine pregnancy test is conducted, then a negative result must be obtained within 24 hours prior to the treatment.

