### **2.8 Follow Up**

#### Group A:

- Subjects may receive a phone call 1 week (1-7 days) after each treatment to record side effects.
- Subjects will return for follow up visits at 30 and 90 days post last treatment.
- Photographs will be taken, adverse events will be documented, and subjects will be asked to complete questionnaires, objective measurements will be taken, and ultrasounds may be performed.
- Any subject affected by COVID-19 that is not able to attend their follow up visits to complete the study will be asked to return to the site for a final follow up visit within 1 year of last treatment.

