## **12.0 SUBJECT WITHDRAWAL**

The subject is free to withdraw from this study at any time. The subject must inform the Investigator immediately if they intend to withdraw. To terminate the subject's participation in this study, they must contact the Investigator at the contact information listed on page one of the informed consent form. They will be asked to come to the study clinic or Investigators office to complete a final follow up visit and may be asked to perform end of study procedures. Their decision to participate in this study or to withdraw from this study will not influence the availability of their future medical care and will involve no penalty or loss of benefits to which they are otherwise entitled.

The Investigator in charge of the study can remove the subject from this study without their consent for any reason, including, but not limited to:

- a) His/her judgment that any condition or circumstance may jeopardize their welfare or the integrity of the study.
- b) Their failure to follow the instructions of the Investigator(s).
- c) If the study is stopped by the sponsor and/or Investigators participating in the study prior to completion.

Data collected prior to withdrawal will be used in data analysis but after withdrawal no further data will be collected.

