- Highly Probable – The event follows a reasonable temporal sequence from the time of investigational product administration; **and** follows a known response pattern to the investigational product; **and** cannot be reasonably explained by other factors such as the subject's clinical state, therapeutic interventions, or concomitant medications administered to the subject; **and** either occurs immediately following investigational product administration, **or** improves on stopping the investigational product, **or** reappears on repeat exposure, **or** there is a positive reaction at the application site.

Each adverse event reported will be graded on a 3-point severity. Using the following definitions for rating severity will be used:

- Mild – easily tolerated, causing minimal discomfort, and not interfering with normal everyday activities.
- Moderate – sufficiently discomforting and may interfere with normal everyday activities.
- Severe – incapacitating and/or preventing normal everyday activities.

**A Serious Adverse Event (SAE)** is any adverse device experience that results in any of the following outcomes: death, a life-threatening adverse device experience, in-patient hospitalization or prolongation of hospitalization, a persistent or significant disability/incapacity, or a congenital anomaly/birth defect. Important medical events that may or may not result in death, be life-threatening, or require hospitalization may be considered a serious adverse device experience when, based upon appropriate medical judgment, they may jeopardize the subject or subject may require medical or surgical intervention to prevent one of the outcomes listed in this definition

If any of the above adverse events are serious as defined by the FDA Code of Federal Regulations (CFR), Title 21, special procedures will be followed. All serious adverse events will be reported within 24 hours of acknowledgment to the Sponsor whether or not the serious events are deemed sampling session-related. All serious event reporting will adhere to 21 CFR part 812 and the IRB will be notified accordingly.

The SAE information will be entered into the database and a desk copy of the complete SAE report will be submitted to the study file.

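### Section 11.0 takes a subject out of the whole study, not only off treatment, when she is or merely suspects she is pregnant, does not tie removal to the available urine test, and leaves tracking of an exposed pregnancy optional

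*Combined protocol and SAP*

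**What the plan says.** Section 11.0 sets the rule: "If she becomes pregnant or thinks that she may be pregnant, she will be removed from the study". She then "will be asked to perform a final evaluation similar to the final follow-up visit"; no timing is given. On the pregnancy itself: "The Investigator may request to track the pregnancy and will report the pregnancy to the Sponsor". Reporting to the Sponsor is therefore mandatory and tracking is not.

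Section 2.6 requires pregnancy verification, including a urine test, before treatments 1 and 5 in Group A. It relies on the date of the last menstrual cycle at the other treatments. It adds: "A urine pregnancy test may also be conducted at the Investigator/clinician's discretion at any time during the study". When a test is done, a negative result is needed in the 24 hours before treatment.

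Section 12.0 covers both voluntary withdrawal and removal by the Investigator. It closes by keeping data gathered so far, but "after withdrawal no further data will be collected". Section 14.0 follows adverse events until they resolve, stabilize, are explained or the subject is lost. Its list of serious outcomes includes "a persistent or significant disability/incapacity, or a congenital anomaly/birth defect".

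For Group A, the Follow Up section says: "Subjects will return for follow up visits at 30 and 90 days post last treatment". For Group B those visits are optional.

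**The concern.** Stopping device exposure on suspicion is protective. Ending observation is a different act, and the rule does not separate the two. It also applies after the last treatment, when there is no exposure left to stop.

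The stake is completeness of the primary objective. Section 1.2 makes adverse events over the whole study the primary objective, and section 3.3 describes an uncleared device with limited safety data. Followed as written, the rule can shorten detection of new events both for a subject whose suspicion proves false and for one who really was exposed while pregnant. The intention-to-treat rule in section 2.15.3 keeps her in the analysis set but cannot supply observations that were never made. Replacement under section 2.11 restores the headcount only.

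The second gap is separate. A birth defect is a serious outcome under section 14.0, but nothing in the protocol requires anyone to ask how an exposed pregnancy ended.

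**Working it through.** The plan gives no figure on this point, so there is none to reproduce. The check has two parts.

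**1. Reading the sections together**

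- *Does a test control removal?* Section 2.6 permits a test at any time, and nothing bars one when a subject reports suspicion. Section 11.0 gives the result no effect: removal follows from pregnancy or from the subject's own belief. Yet section 2.6 accepts a negative test as sufficient to go ahead with treatment.
- *Does removal end observation?* Section 12.0 deals with removal by the Investigator as well as voluntary exit, so its closing sentence is reasonably read as applying here. What remains is the one final evaluation, any tracking the Investigator chooses to request, and follow-up of events already open (sections 2.14 and 14.0). Scheduled detection of *new* events stops.
- *Does another section require follow-up to pregnancy outcome?* Section 14.0 follows adverse events, and pregnancy is not named as one. The report to the Sponsor in section 11.0 carries no duty to follow the outcome. No section requires it.

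**2. Post-exposure observation lost, Group A**

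Inputs from the Group A schedule in section 2.12: treatments 7 days apart (±4); follow-up at 30 days (±10) and 90 days (±10) after the last treatment. Assumption: the final evaluation takes place at once on removal.

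Loss = day of the 90-day visit − day of removal, both counted from the last treatment received.

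| Removed | Nominal loss | With visit windows |
|---|---|---|
| Near day 90 | 90 − 90 = 0 days | – |
| At the 30-day visit | 90 − 30 = 60 days | 80 − 40 = 40 to 100 − 20 = 80 |
| When the next weekly treatment is due | 90 − 7 = 83 days | 80 − 11 = 69 to 100 − 3 = 97 |

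A subject who reports suspicion before the next treatment is due loses up to 7 days more than the nominal 83. A later final evaluation makes every loss smaller. Group B cannot be bounded, because its follow-up visits are optional.

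Share per removal: 1/20 = 5.0% on the sample size in section 2.15.2; 1/30 = 3.3% on the enrolment ceiling in section 2.1. The documents give no pregnancy rate, so no expected number of removals can be calculated. The exclusion criteria and section 2.6 should keep it low.

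**The case against.** The best defence is that automatic removal is a deliberate precaution. The device is uncleared, benefit to the subject is uncertain, and a sponsor may prefer a simple rule. An investigator can test at any time, and section 15.0 allows a deviation approved by the Sponsor and the IRB, which could keep a subject whose test is negative. Part of this stands: halting treatment on suspicion is right. But the deviation route is ad hoc, and the precaution does not require ending observation.

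A second objection is stronger. The follow-up visits involve no treatment, but they are not free of physical demand. The schedule lists an optional abdominal strength test at both visits, and section 2.13 describes it as a held sit-up against pressure to the subject's limit. Removal spares a possibly pregnant subject that test. This stands and shapes the fix.

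Third, the Sponsor, once told of a pregnancy, can pursue it, and section 14.0 ties reporting of an unanticipated device effect to when the investigator learns of it, not to a visit. A birth defect could therefore reach the Sponsor without formal tracking. That is a real second route, but weaker than a routine request. The consent form, the Sponsor's procedures and the Monitoring Plan might also cover tracking or later contact; they are not available to check.

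A reader might go further and infer that a removed subject's safety data are lost altogether, that the protocol forbids a confirming test, or that pregnancies go unreported. The text supports none of these: open events are followed, a final evaluation is requested, testing is allowed and reporting is mandatory. A reader might also measure the harm by the time between the last visit and a birth. That does not measure this defect, because a 90-day follow-up would not capture most births even with the removal rule repaired.

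**Conclusion.** The point holds as a minor one and is best labelled a cheap improvement. Section 11.0 joins stopping treatment to ending follow-up, lets unconfirmed suspicion trigger both, and leaves tracking of an exposed pregnancy to discretion.

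The size is roughly 0 to 83 days of post-exposure observation per affected Group A subject, with each removal being 3.3% to 5.0% of the sample. This rests on an immediate final evaluation and on reading the closing sentence of section 12.0 as applying to removal for pregnancy. Few subjects are likely to be involved.

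It would be wrong to infer a threat to any inferential result. Section 2.15.6 summarizes safety data without statistical comparison, so the effect is on completeness of the safety record only. The conclusion concerns the protocol text and not what the unseen consent form or procedures may add.

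**What to change.** Amend section 11.0 as follows.

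- **On suspicion:** hold treatment and perform the urine test already available under section 2.6, repeated if needed. If pregnancy is not confirmed, the subject continues in the study.
- **If confirmed:** stop treatment permanently, but keep adverse event follow-up at 30 and 90 days after the last treatment, by visit or call. State this as an exception to the last sentence of section 12.0.
- **Strength test:** do not perform it while pregnancy is suspected or confirmed.
- **Efficacy data:** do not use any efficacy measure taken during a confirmed pregnancy. That covers photographs, GAIS, satisfaction, circumference, weight, ultrasound and strength.
- **Tracking:** make the request mandatory for every confirmed pregnancy, through to its outcome, with the subject's agreement. This makes the request certain; the outcome still depends on her agreement.

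The cost is a few sentences of protocol wording, possibly matching consent wording, and a few extra visits or calls for a rare event. Attribution becomes harder for some events, because swelling, soreness and cramping are also anticipated device effects in section 2.14; the pregnancy should be noted when relatedness is rated. The efficacy measurements given up would have been confounded by the pregnancy in any case.
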